An international multicenter, randomised, double-blind, placebo-controlled parallel-group clinical study of efficacy and safety of various schemes of Tenoten® in the treatment of anxiety in subjects with somatoform, stress-related disorders and other neurotic disorders

Phase IV

Sponsor

OOO «NPF «MATERIA MEDICA HOLDING»

Protocol numberMMH-TN-001Version date:April 19, 2016ClinicalTrials.gov Id:NCT03036293

Protocol Summary

This document represents the protocol summary for the study on human subjects. The study will be carried out in accordance with ICH GCP, National Standard of the Russian Federation GOST 52379-2005 "Good Clinical Practice", Helsinki Declaration of World Medical Association, relevant requirements of the regulatory authorities as well as the study procedures.

Title of Study

An international multicenter randomized double-blind placebo-controlled parallel-group clinical study of efficacy and safety of various schemes of Tenoten in the treatment of anxiety in subjects with somatoform, stress-related disorders and other neurotic disorders

Phase: IV

Sponsor: OOO "NPF "Materia Medica Holding", Moscow, Russia *Protocol No.* MMH-TN-001

Objective of the study

- To obtain additional efficacy and safety data for various schemes of Tenoten® dosing in the treatment of anxiety in subjects with somatoform, stress-related or other neurotic disorders.
- To compare efficacy of the two schemes of Tenoten® dosing (daily dose of 4 and 8 tablets for 12 weeks) in the treatment of anxiety in subjects with somatoform, stress-related or other neurotic disorders.

Endpoints

Primary endpoint

- 1. Change from baseline in mean HAM-A score after 12 weeks of treatment.
 - 1. group 1 (Tenoten® 4 tablets a day)
 - 2. group 3 (Tenoten® 8 tablets a day).

Secondary endpoints

1. Change from baseline in mean HAM-A score after 4 weeks of treatment:

1.1. group 1 (Tenoten® 4 tablets a day)

- 1.2. group 3 (Tenoten® 8 tablets a day).
- 2. Change from baseline in mean HAM-A score after 8 weeks of treatment.

2.1. group 1 (Tenoten[®] 4 tablets a day)

2.2. group 3 (Tenoten® 8 tablets a day).

 Proportion of the subjects with reduced anxiety by ≥ 50% according to HAM-A scale vs. baseline:

3.1. group 1 (Tenoten® 4 tablets a day)

- 3.1.1. after 4 weeks of therapy
- 3.1.2. after 8 weeks of therapy
- 3.1.3. after 12 weeks of therapy
- 3.2. group 3 (Tenoten® 8 tablets a day)
 - 3.2.1. after 4 weeks of therapy
 - 3.2.2. after 8 weeks of therapy

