 - 3.2.3. after 12 weeks of therapy.
- 4. Proportion of subjects with lack of anxiety (<14 points according to HAM-A scale):
 - 4.1. group 1 (Tenoten® 4 tablets a day)
 - 4.1.1. after 4 weeks of therapy
 - 4.1.2. after 8 weeks of therapy
 - 4.1.3. after 12 weeks of therapy
 - 4.2. group 3 (Tenoten® 8 tablets a day)
 - 4.2.1. after 4 weeks of therapy
 - 4.2.2. after 8 weeks of therapy
 - 4.2.3. after 12 weeks of therapy.
- 5. Change from baseline in total EQ-5D-3L score after 12 weeks of treatment.
 - 5.1. group 1 (Tenoten® 4 tablets a day)
 - 5.2. group 3 (Tenoten® 8 tablets a day).
- 6. Total CGI score:
 - 6.1. group 1 (Tenoten® 4 tablets a day)
 - 6.2. group 3 (Tenoten® 8 tablets a day).

Safety assessment

- Occurrence and nature of adverse events, their intensity (severity), causal relationship to the study drug, and outcome.
- Changes in vital signs during the treatment.

Study design

Design – an international multicenter, randomized, double-blind, placebo-controlled parallelgroup clinical trial to evaluate efficacy and safety of various schemes of Tenoten \mathbb{R} in the treatment of anxiety.

The study will enroll outpatient subjects of both genders aged 18-45 years with verified diagnoses of somatoform, stress-related and other neurotic disorders (F43, F45, F48) and signs of clinically relevant anxiety according to The Hospital Anxiety and Depression scale (HADS). After signing information sheet (informed consent form) to participate in the clinical study the subject will be interviewed (complaints, medical history, concomitant therapy) and physical examination will be performed; the subject will fill HADS scale. Degree of anxiety at screening should be ≥ 11 according to HADS. Where the subject meets inclusion criteria and has no exclusion criteria he/she will be enrolled into the study. The investigator will determine degree of anxiety using HAM-A scale; the subject will fill EQ-5D-3L questionnaire. At Visit 1 (Day 1) the subject will be randomized into one of the follow treatment groups:

- Group 1: Tenoten[®] at 2 tablets twice daily (4 tablets/day);
- Group 2: Placebo at 2 tablets twice daily (4 tablets/day);
- Group 3: Tenoten® at 2 tablets 4 daily (8 tablets/day).
- Group 4: Placebo at 2 tablets 4 daily (8 tablets/day).

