The first dose of the study drug should be administered at Visit 1 after the visit procedures are completed. Further administration of the study product will be made according to the dosing scheme. The subject will administer the study drug and will be followed for 12 weeks during which additional three visits will be made. At Visit 2 (Week 4), Visit 3 (Week 8) and Visit 4 (Week 12) the physician will record patients' complaints and physical examination data, fill HAM-A scale, check the study and concomitant therapy, assess treatment safety and patient compliance with the study treatment. At the final Visit 4 the subject will fill EQ-5D-3L questionnaire and the investigator will determine Clinical Global Impression Scale Efficacy Index (CGI-EI) score.

The patients will be allowed to take symptomatic therapy and medications for their comorbidities during the study, except for the medicines listed in "Forbidden concomitant therapy".

Inclusion and exclusion criteria

Inclusion criteria

- 1. Age between 18 and 45 years old inclusively.
- 2. Diagnosis of somatoform, stress-related and other neurotic disorders (F43, F45, F48)¹ established according to ICD-10 study diagnostic criteria.
- 3. Clinically relevant anxiety at screening (≥ 11 points according to HADS scale).

¹ Diagnosis of diseases and diagnostic procedures to verify somatoform, stress-related and other neurotic disorders in the subjects will not be the study objective; the diagnostics algorithm will be defined by the investigator.

- 4. Availability of signed patient information sheet (Informed Consent form) for participation in the clinical trial.
- 5. Usage of contraceptive methods² by both gender patients of reproductive age during the trial and within 30 days of ending the participation in the trial.

Exclusion criteria

- 1. Expressed depression symptoms at screening (≥ 11 points according to HADS scale).
- 2. Organic including symptomatic, mental disorders (F00-09).
- 3. Mental disorders or behavioural disorders associated with psychoactive substances (F10-19).
- 4. Schizophrenia, schizotic conditions and delusional disorders (F20-29).
- 5. Mood disorders [affective disorders] (F30-39).
- 6. Phobic (F40) and other anxiety disorders (F41), obsessive-compulsive disorder (F42), dissociative [conversion] disorders (F44), depersonalization syndrome (F48.1).
- Behavioural syndromes associated with physiological disorders and physical factors (F50-59).

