Procedure/visit	Visit 1 (Day 1)	Visit 2 (Week 4±3 days)	Visit 3 (Week 8±3 days)	Visit 4 (Week 12±3 days)
Informed consent	+			
Collection of complaints	+	+	+	+
Medical history	+			
Physical examination	+	+	+	+
HADS scale filling	+			
HAM-A scale filling	+	+	+	+
EQ-5D-3L questionnaire filling	+			+
Pregnancy test	+			
Concomitant therapy	+	+	+	+
Inclusion/exclusion criteria	+			
Randomization and prescription of study therapy	+			
Study drug supply	+	+	+	
Study drug accountability, compliance assessment		+	+	+
CGI scale filling				+
Evaluation of treatment safety		+	+	+

Schedule of study procedures

Statistical Analyses

Samples

Total set includes all the subjects who have signed ICF. This sample will consider all adverse events throughout the study, including those occurred prior to the study therapy.

The sample including all subjects who received at least one dose of the study product to be used for *analysis of the study treatment safety and tolerability* (*Safety population*), as all adverse events identified after the study product administration will be recorded.

Full Analysis Set This sample will consist of all enrolled subjects, except for those who met at least one of the following criteria:

- 1) failure to meet inclusion/non-inclusion criteria;
- 2) subject failing to take any dose of the study drug;
- 3) absence of any data on the subject after the study drug administration.

This was the best set for the Intention-to-treat method, so it will be used in the *Intention-to-treat efficacy analysis of the test therapy*.

Per Protocol set. This sample includes all subjects who completed the therapy as per the study protocol, without any missing visits or major protocol deviations. This set will be used in the *Per*

Protocol efficacy analysis of the test therapy.

Mean value of the total set for the relevant day will be used to fill lacking/missing data.

Data treatment and all statistical calculations under the protocol will be made using SAS-9.4 statistical software.¹⁰

Evaluation of sample size

The sample size was assessed in accordance with the following rules and assumptions:

- 1. Statistical assumptions
 - 1.1 the power of statistical tests 'P = (1β) ' is 80% (the probability of correct rejection of the null hypothesis is 0.8)
 - 1.2 the probability of type 1 error 'a' is less that 5% (the probability of false acceptance of the alternative hypothesis is less than 0.05);

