Mean HAM-A total score at 12 weeks of therapy in Tenoten groups with both dosing schemes is expected to reduced by at least 10 units, in Placebo - by no more than 6 units (difference – at least 4 points). Population variance for total score change was $\sigma^2=44$ (based on preliminary analysis).

HAM-A mean score changes after 12 weeks in Tenoten groups for both dosing schemes are expected to differ by less than **3** points. Population variance was accepted as 6^2 =44 (based on preliminary analysis).

According to the statistical criteria and the assumptions above, for evaluation of differences in various dosing schemes, group size will be **103** subjects for Tenoten group (each dosing scheme) and **52** subjects for Placebo group (each dosing scheme). To evaluate superiority of the study product over placebo at different dosing schemes the group size will be 58 subjects for Tenoten group (each dosing scheme) and 26 subjects for Placebo group (each dosing scheme). The final sample size will be **103** subjects for Tenoten groups (each dosing scheme) and **52** subjects for Placebo group (each dosing scheme).

Given potential withdrawal of at least 20% subjects during the study for various reasons, at least **390** subjects will be required to sign informed consent.

Statistical criteria

All statistical calculations will be made using two groups of statistical criteria:

- parametric to evaluate continuous and interval random values;
- nonparametric to obtain:
 - evaluations of equality/inequality of proportions of the subjects upon their comparison for various visits,

- analysis of frequencies of the features compared, and
- evaluation of continuous and interval random values in case of non-compliance with normal random distribution.

Parametric criteria

Prior to analysis using parametric statistics, data samples under comparison will be tested for normality (the Kolmogorov-Smirnov test). Data normalizing transformations (e.g. Box-Cox, Yeo-Johnson etc.) would be applied if necessary.

The following parameters and approaches are to be used:

- 1. To evaluate the differences in continuous variables obtained in one group at two different visits Student's test for matched samples.
- 2. To evaluate time changes in parameters compared analysis of variance (ANOVA) or modified repeated measures covariance (ANCOVA).

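### Secondary endpoint 4 (HAM-A below 14) has no baseline condition although entry is set by HADS, so its rates can include subjects who already met it before the first dose; adjust for baseline HAM-A and report the baseline count

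*Combined protocol and SAP*

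**What the plan says.** The combined protocol and SAP lists as secondary endpoint 4 the "Proportion of subjects with lack of anxiety (<14 points according to HAM-A scale", for each Tenoten dosing scheme at weeks 4, 8 and 12. That makes six reported proportions, with no condition on the baseline score. The neighbouring endpoint 3 does refer to baseline: "Proportion of the subjects with reduced anxiety by ≥ 50% according to HAM-A scale vs. baseline".

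Anxiety severity at entry rests on another instrument. Inclusion criterion 3 reads "Clinically relevant anxiety at screening (≥ 11 points according to HADS scale", and the Study design section repeats it: "Degree of anxiety at screening should be ≥ 11 according to HADS". That section then states "Where the subject meets inclusion criteria and has no exclusion criteria he/she will be enrolled into the study", and only afterwards "The investigator will determine degree of anxiety using HAM-A scale; the subject will fill EQ-5D-3L questionnaire". No minimum HAM-A score is attached. None of the 5 inclusion or 23 exclusion criteria mentions HAM-A.

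Under Samples, the Full Analysis Set drops subjects for "failure to meet inclusion/non-inclusion criteria", for taking no dose, or for having no data after dosing. The Per Protocol set requires completion without missed visits or major deviations. Neither removes a subject with a low baseline HAM-A.

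Under Non-parametric criteria, 2×2 tables go to chi-square or Fisher's exact test. Cochran-Mantel-Haenszel and survival analysis are also listed, and GENMOD appears under Parametric criteria. None of these is assigned to endpoint 4 by name, and no stratum or baseline covariate is specified for it.

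**The concern.** The schedule of procedures places HADS and HAM-A at the same Visit 1. A subject can therefore be enrolled for clinically relevant anxiety on HADS and, on the same day, already satisfy the protocol's HAM-A definition of no anxiety. A subject at 12 who stays at 12 is then counted at weeks 4, 8 and 12 without having improved.

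What is at stake is mainly interpretation. Readers are likely to take these proportions as anxiety that resolved on treatment, while an unknown part may have been present before the first dose. The plan does not ask for the number below 14 at baseline, so the two could not be separated. A lesser matter is efficiency: an unadjusted 2×2 test ignores a baseline score that is collected anyway and is probably prognostic.

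**Working it through.** The plan states no rate, power or sample size for endpoint 4, so there is no figure to reproduce. What follows is an illustration on assumed inputs.

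**Inputs**
- Baseline mean M: not stated. The sample-size section sets the equivalence margin at 0.15·M and gives 3 points for the difference between dosing schemes. If 3 is the margin, M = 3/0.15 = 20. The stated 103 per Tenoten group does arise with 3 in the denominator: 2(1.960 + 1.282)²·44/3² = 102.7. M is varied from 16 to 24.
- Baseline SD: not stated. "Population variance for total score change was" 44. With equal variances at both visits and correlation ρ, 44 = 2·SD²·(1 − ρ), so SD = √(22/(1 − ρ)). This is 4.69 at ρ = 0, 5.61 at ρ = 0.3 and 6.63 at ρ = 0.5.
- Mean reductions: 10 (Tenoten) and 6 (placebo), from the expected effects.

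**Share below 14 at baseline**, Φ((cut − M)/SD):
- M = 20, cut at 14: Φ(−6/4.69) = 10.0%; Φ(−6/6.63) = 18.3%.
- M = 20, cut at 13.5 because scores are whole numbers: 8.3% and 16.4%.
- Taken together this is about 8% to 18%, or 32 to 71 of 390 subjects.
- M = 24, SD 4.69, cut 13.5: about 1%. M = 16, SD 6.63, cut 14: about 38%.

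**Effect on the week-12 result** (bivariate normal, M = 20, cut at 14):

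| ρ | Tenoten vs placebo, all subjects | Difference | Baseline ≥14 only | Difference | Share of successes already below 14 (Tenoten, placebo) |
|---|---|---|---|---|---|
| 0 | 80.3% vs 50.0% | 30.3 | 80.3% vs 50.0% | 30.3 | 10%, 10% |
| 0.3 | 76.2% vs 50.0% | 26.2 | 74.1% vs 46.9% | 27.2 | 17%, 20% |
| 0.5 | 72.7% vs 50.0% | 22.7 | 68.1% vs 43.5% | 24.6 | 23%, 29% |

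Rates fall by 0 to 7 points on restriction, but they fall in both arms, so the contrast moves by 0 to 2 points. With the cut at 13.5 and ρ = 0.5 the pattern is the same: 70% vs 47% becomes 66% vs 41%. The shift depends on M. At ρ = 0.5 and cut 13.5 it is about 3 points at M = 18 (20.7 to 23.6) and almost nothing at M = 24 (22.1 to 22.2). At M = 16 it reaches 4 to 5 points.

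**Cost of restricting versus adjusting**
- The 390 subjects split into 130 per Tenoten group and 130 pooled placebo. At ρ = 0.5, z = difference/√{[p₁(1−p₁) + p₀(1−p₀)]/n}. All subjects, n = 130: 0.227/0.0587 = 3.86. Baseline ≥14 only, n = 130 × 0.817 = 106: 0.246/0.0660 = 3.73. At ρ = 0 the values are 5.41 and 5.13. The loss of subjects outweighs the gain in difference.
- Simulation with a smaller assumed effect (reductions 8 and 6, M = 20, ρ = 0.5, 103 vs 104 subjects, two-sided 0.05, 4,000 trials): power about 0.40 unadjusted, 0.38 restricted, 0.46 by logistic regression with baseline HAM-A. A second run at the same correlation, also with a reduced effect, gave 0.41, 0.37 and 0.45.

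**The case against.** The best defence is that endpoint 4 describes a status at a visit, not a conversion. Endpoint 3 and the change scores already cover improvement from baseline, and randomisation balances low-baseline subjects in expectation. All of that stands. It answers the question of bias, but it does not tell the reader how much of the reported status predates treatment.

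Several stronger readings are tempting and are not supported:
- *That everyone below 14 at baseline is a success.* Such a subject counts only if still below 14 at the visit; one who worsens to 14 or more does not.
- *That the treatment effect is materially diluted or one arm favoured.* At M = 20 the contrast moves by at most 2 points, and at ρ = 0 by none. Even the inflation of rates disappears at ρ = 0.
- *That chance imbalance passes straight into the comparisons.* Its SD for the share below 14 is √(2p(1−p)/130), or 3.7 to 4.8 points for p of 10% to 18%. That is ordinary sampling variation, reflected in the test's standard error, and it reaches the endpoint only in part.
- *That 10% or 18% of subjects will start below 14.* Mean, SD and correlation are assumptions, and requiring HADS of at least 11 may thin the lower tail.

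It is also fair to say that the plan lists methods able to use baseline (Cochran-Mantel-Haenszel, GENMOD). They are available, but they are not assigned to this endpoint.

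**Conclusion.** The structural point holds on the text: HADS decides entry, HAM-A below 14 decides success, and nothing requires a HAM-A of 14 or more at baseline. The consequence is limited to how the six raw proportions are read, and to some avoidable loss of precision. There is no systematic advantage to any arm, no inflation of type I error and no effect on the primary endpoint or the sample size.

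The extent cannot be known from the documents. The figures above rest on normality, equal variances at the two visits, a variance of change of 44 and an assumed mean. They matter most if the baseline mean is low and the correlation substantial, and hardly at all if the mean is near 24 or the correlation near zero. This is a low-cost improvement to a secondary endpoint, not a flaw in the trial's main conclusion.

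**What to change.** In the SAP text for secondary endpoint 4:
1. Make the main analysis a logistic regression in all subjects of the analysis set, with treatment group and baseline HAM-A (continuous) as terms, in place of the unadjusted chi-square or Fisher test. GENMOD is already listed, but the text ties generalized models to non-normal data, so its use here should be stated.
2. Report the number and percentage of subjects with baseline HAM-A below 14 in each arm. Adjustment improves the comparison but leaves the raw rates as they are, so this count is needed to interpret them.
3. Show the proportion below 14 among subjects with baseline HAM-A of at least 14 as a supportive display only. As the main analysis it would discard roughly 8% to 18% of subjects under the M = 20 assumptions and lose power.

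The cost is SAP wording and one extra table. Baseline HAM-A is already collected at Visit 1, no subjects are lost, and neither eligibility nor sample size changes.

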- 8. Personality and behavioural disorders at mature age (F60-69).
- 9. Mental deficiency (F70-79).
- 10. Inflammatory and traumatic injuries of brain with persistent neurological deficit.
- 11. Prior diagnosis of heart failure defined by the New York Heart Association classification (1964) as III or IV FC.
- 12. Malignant neoplasm/suspected malignant neoplasm
- 13. Patients allergic to/intolerant of any constituent of the medications used in the treatment.
- 14. Malabsorption syndrome, including congenital or acquired lactase deficiency (or any other disaccharidase deficiency) and galactosemia.
- 15. Any conditions which, according to the investigator, may interfere with the subject's participation in the study.
- 16. Scheduled hospiralizations, surgeries during the study.
- 17. Patients who, from the investigator's point of view, will not comply with the observation requirements of the study or adhere to study drug dosing regimens.
- 18. Use of any medicine listed in the section "Prohibited concomitant treatment" within 30 days preceding the inclusion in this study.
- 19. Drug addiction, alcohol usage in the amount exceeding 2 units of alcohol per day³.
- 20. Pregnancy, breast-feeding.

² Acceptable contraception includes intrauterine device; barrier method (condom, contraceptive cap, cervical cap or spermicide), previous surgical sterilization or vasectomy (for male subjects or partners). Throughout the study systemic hormonal contraceptives including oral contraceptives will not be allowed.

³1 unit of alcohol is equivalent to 0.33 L of lager/150 mL of unfortified wine, or 40 mL of a spirit

- 21. Participation in other clinical trials in the previous 3 months.
- 22. Patients who are related to any of the on-site research personnel directly involved in the conduct of the trial or are an immediate relative of the study investigator. 'Immediate relative' means husband, wife, parent, son, daughter, brother, or sister (regardless of whether they are natural or adopted).
- 23. Patients who work for OOO "NPF "Materia Medica Holding" (i.e. the company's employees, temporary contract workers, appointed officials responsible for carrying out the research or immediate relatives of the aforementioned).

Criteria for Withdrawal or Termination

- 1. Participant's failure or decline to comply with the protocol requirements.
- 2. Necessity for prescribing medications not permitted during the study.

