- 3. An adverse event requiring discontinuation of the study product;
- 4. Pregnancy.
- 5. Patient's decision to withdraw early for lack of efficacy or other reasons.
- 6. Eligibility error.
- 7. Cases not stipulated in the protocol where the investigator decides that further participation may harm the patient.

Number of subjects

It is planned to include 390 subjects, which is expected to yield at least 310 patients completing all protocol procedures.

Interim analysis

An interim statistical analysis is not scheduled within the study.

Treatment

Group 1

Name of the medicinal product: Tenoten

Active ingredient: Affinity purified antibodies to brain-specific S-100 protein - 0.003 g*

* applied onto lactose as a water-alcohol mixture containing no more than 10^{-15} ng/g active form of the API.

Excipients: Lactose monohydrate (lactose) - 0.267g (Eur. Ph.⁴, USP⁵ NF, BP⁶)

Microcrystalline cellulose - 0.03 g (Eur. Ph., USP NF, BP)

Magnesium stearate - 0.003 g (Eur. Ph., USP NF, BP)

⁴ Eur. Ph. European Pharmacopoeia (current edition)

⁵ USP – current US Pharmacopeia

⁶ EP – current European Pharmacopoeia

Method of administration: Tablet for oral use. Dose per administration: 2 tablets. 2 tablets twice daily (4 tablets/day). The tablets should be held in the mouth until dissolution, without meal.

Dosage form: Tablets.

Description: White to off-white, round, flat, scored on one side and beveled tablets.

Storage conditions: Store in a place protected from light at a temperature below 25 C. Keep out of the reach of children.

Group 2

Name of the medicinal product: Placebo

Active ingredient: NA

Excipients: Lactose monohydrate (lactose) - 0.267 g (Eur. Ph⁴., USP⁵ NF, BP⁶)

Microcrystalline cellulose - 0.03 g (Eur. Ph., USP NF, BP)

Magnesium stearate - 0.003 g (Eur. Ph., USP NF, BP)

Method of administration: Tablet for oral use. Dose per administration: 2 tablets. 2 tablets twice daily (4 tablets/day). The tablets should be held in the mouth until dissolution, without meal.

Dosage form: Tablets.

Description: White to off-white, round, flat, scored on one side and beveled tablets.

Storage conditions: Store in a place protected from light at a temperature below 25 C. Keep out of the reach of children.

Group 3

Active ingredient: Affinity purified antibodies to brain-specific S-100 protein - 0.003 g* * *applied onto lactose as a water-alcohol mixture containing no more than* 10^{-15} ng/g active form of the API.

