Excipients: Lactose monohydrate (lactose) - 0.267g (Eur. Ph.⁷, USP⁸ NF, BP⁹)

Microcrystalline cellulose - 0.03 g (Eur. Ph., USP NF, BP)

Magnesium stearate - 0.003 g (Eur. Ph., USP NF, BP)

Method of administration: Tablet for oral use. Dose per administration: 2 tablets. 2 tablets 4 times daily (8 tablets/days). The tablets should be held in the mouth until dissolution, without meal.

Dosage form: Tablets.

Description: White to off-white, round, flat, scored on one side and beveled tablets.

⁷ Eur. Ph. European Pharmacopoeia (current edition)

⁸ USP – current US Pharmacopeia

⁹ EP – current European Pharmacopoeia

Protocol No. MMH-TN-001 19-Apr-2016 Storage conditions: Store in a place protected from light at a temperature below 25 C. Keep out of the reach of children.

Group 4

Name of the medicinal product: Placebo

Active ingredient: NA

Excipients: Lactose monohydrate (lactose) - 0.267 g (Eur. Ph⁴., USP⁵ NF, BP⁶)

Microcrystalline cellulose - 0.03 g (Eur. Ph., USP NF, BP)

Magnesium stearate - 0.003 g (Eur. Ph., USP NF, BP)

Method of administration: Tablet for oral use. Dose per administration: 2 tablets. 2 tablets 4 times daily (8 tablets/days). The tablets should be held in the mouth until dissolution, without meal.

Dosage form: Tablets.

Description: White to off-white, round, flat, scored on one side and beveled tablets.

Storage conditions: Store in a place protected from light at a temperature below 25 C. Keep out of the reach of children.

Treatment duration

Tenoten/Placebo treatment duration is 12 weeks.

Observation period

In total the patients will be monitored for 12 weeks.

Symptomatic (Standard) treatment

Subjects are allowed to receive medications used to treat coexisting diseases other than those representing exclusion criteria, except drugs listed in section "Forbidden concomitant therapy".

Prohibited concomitant therapy

Within 4 weeks prior to enrollment and during the study (beginning from signing informed consent form and initiation of screening) subjects are not allowed to receive any medications that may affect mental and emotional status (parenthesized is the ATC group):

- 1. Psycholeptics (ATC group N05), including antipsychotics, anxiolytics (tranquilizers), hypnotics and sedatives.
- 2. Psychoanaleptics (ATC group N06) including antidepressants, psychostimulants, nootropic drugs and their combinations.
- 3. Antiepileptic drugs (ATC group N03A).
- 4. Anticholinergic drugs (ATC group N04A).

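### Up to about one in five Week 12 HAM-A scores may be missing, an unstated share because of poor response, and the plan schedules no HAM-A at or after withdrawal

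*Combined protocol and SAP*

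**What the plan says.** All references are to the combined protocol and SAP.

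- **Criteria for Withdrawal or Termination.** Seven criteria form a single list, which does not distinguish stopping the drug from leaving the study. Item 2 is "Necessity for prescribing medications not permitted during the study" and item 5 is "Patient's decision to withdraw early for lack of efficacy or other reasons". Others, such as pregnancy and "Eligibility error", have nothing to do with response.
- **Prohibited concomitant therapy.** The list includes "Psycholeptics (ATC group N05), including antipsychotics, anxiolytics (tranquilizers), hypnotics and sedatives", and antidepressants as well. Item 2 can therefore be met by a subject whose anxiety has not improved.
- **Schedule of study procedures.** HAM-A is done at Visits 1 to 4 (Day 1 and Weeks 4, 8 and 12). No early-termination visit is shown, and no assessment of a withdrawn subject.
- **Number of subjects; Evaluation of sample size, item 2.** 390 subjects are to yield at least 310 completers. The stated reason is "Given potential withdrawal of at least 20% subjects during the study for various reasons", and the 390 are those who "subjects will be required to sign informed consent".
- **Statistical Analyses, Samples.** "Mean value of the total set for the relevant day will be used to fill lacking/missing data". The total set is everyone who signed consent, so the filled value is the same in every arm. The Full Analysis Set drops eligibility failures, subjects never dosed and subjects with no post-dose data. The Per Protocol set drops anyone with a missed visit.

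**The concern.** A subject who needs an anxiolytic, or who gives up because the tablets do not help, is likely to differ at Week 12 from one who stays. If that subject's Week 12 score is never taken, neither efficacy set contains it: the Per Protocol set omits the subject, and the Full Analysis Set puts in a number that does not depend on treatment or on how the subject fared. No sensitivity analysis for missing data is described.

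When arms lose different fractions of subjects for such reasons, the estimated drug-placebo difference moves away from the difference among all subjects. Which way it moves depends on which arm loses more, and this cannot be known in advance. At stake is the primary endpoint, the change in HAM-A at 12 weeks.

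**Working it through.** **1. The plan's own loss figure.** Completers: 2 × 103 + 2 × 52 = 310. The plan's formula N_T = N_PP/(1 − C_w) gives 310/0.80 = 387.5, so 388; the stated 390 agrees closely. Expected loss is (390 − 310)/390 = 80/390 = 20.5%, all causes.

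**2. The share tied to response.** The documents give no split by reason. If 25%, 50%, 75% or 100% of losses were tied to response (an assumed range), that is 20, 40, 60 or 80 subjects, or 5%, 10%, 15% or 21% of 390.

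**3. Bias when loss is unequal.** Inputs from Evaluation of sample size, item 2: mean reduction 10 on Tenoten (both schemes) and 6 on placebo, taken here as the completers' means. Two Tenoten groups and a pooled placebo group of about equal size follow from items 1.5 and 1.6. Assumptions: loss fractions f_T and f_P, total loss 20%; mean change w among withdrawn subjects, the same in every arm; the fill treated as a constant change c, which in mean terms requires equal baselines.

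- Pooled constant: c = [2(1 − f_T)·10 + (1 − f_P)·6] / [2(1 − f_T) + (1 − f_P)]
- Filled difference: (1 − f_T)·10 + f_T·c − (1 − f_P)·6 − f_P·c
- True difference among all subjects, whether or not they stopped drug: the same with w in place of c
- Bias, filled minus true: (f_T − f_P)(c − w)

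At 15%/30% and w = 0: c = (17 + 4.2)/2.4 = 8.83. Filled = 9.825 − 6.850 = 2.975 (quoted as 2.97). True = 8.5 − 4.2 = 4.30.

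At 25%/10% and w = 0: c = (15 + 5.4)/2.4 = 8.50. Filled = 9.625 − 6.250 = 3.375 (quoted as 3.38). True = 7.5 − 5.4 = 2.10.

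| Loss, Tenoten/placebo | Filled | Completers only | True (w = 0) | 75% of lost values collected |
|---|---|---|---|---|
| 20%/20% | 3.2 | 4.0 | 3.2 | 3.2 |
| 15%/30% | 2.97 | 4.0 | 4.30 | 4.02 |
| 25%/10% | 3.38 | 4.0 | 2.10 | 2.37 |

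In the last column the remaining quarter is still filled with the pooled mean. For 15%/30%, for example, 3.75% and 7.5% stay missing, c = 21.2/2.85 = 7.44, and the estimate is 8.5 + 0.28 − 4.2 − 0.56 = 4.02.

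The bias shrinks as withdrawn subjects do better. With w = 3 the true differences are 3.85 and 2.55; with w = 6 they are 3.40 and 3.00. The filled values stay at 2.97 and 3.38.

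**4. What the fill does by itself.** Now let loss be unrelated to outcome, 20% in every arm. The 4-point difference becomes 0.8 × 4 = 3.2. For equivalence take 130 per Tenoten arm, variance 44 and a margin of 3 points. The plan sets the margin at 0.15·M without giving M, so 3 is an assumption; it corresponds to M = 20. A true 3-point dose difference becomes 0.8 × 3 = 2.4, with SE = √(0.8 × 2 × 44/130) = 0.736. False equivalence is Φ(0.6/0.736 − 2.128) = 9.5% at 0.05/3, or Φ(0.6/0.736 − 1.960) = 12.6% at 0.025. If the missing values are simply left out, simulation gives 4.0 points and false equivalence close to nominal (1.5% to 1.9% at 0.05/3 in two runs). These distortions therefore come from the fill rule, not from the absence of follow-up.

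**The case against.** **Is the whole one in five tied to response?** A reader might infer this from the withdrawal criteria. The documents do not support it. The 20% covers various reasons, several criteria are unrelated to response, and item 2 also covers prohibited drugs needed for reasons other than anxiety. The count starts at consent, and some of those lost leave the Full Analysis Set rather than being filled. So 80 is an upper bound for filled scores, and the response-related share is unknown.

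**Does the withdrawal rule cause the shrinkage to 3.2 points and the excess false equivalence?** This too is tempting, but step 4 shows otherwise. Those figures assume loss unrelated to outcome and disappear once the pooled fill is dropped, without a single extra visit. They belong to the separate defect in the fill rule. For superiority under equal loss, the fill shrinks estimate and standard error together, so it does not by itself inflate type I error.

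**Does the plan forbid later assessment?** No. The document is a protocol summary, says subjects are followed for 12 weeks, and is silent on assessment after withdrawal. Silence still gives sites no instruction to obtain the score.

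**Would collected values help?** Off-drug values can draw arms together legitimately. If withdrawn subjects reduced by 6 points in every arm (an assumption) and all values were collected, the difference would be (0.8 × 10 + 0.2 × 6) − 6 = 3.2, no larger than with the fill. This stands. The gain is not a larger effect but an estimate that answers a defined question: the effect regardless of stopping drug. Choosing that question has to be stated openly.

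**Is the Per Protocol analysis a safeguard?** It is undistorted when loss is unrelated to outcome. Under the response-related loss in step 3 it gives 4.0 whether the all-subject difference is 4.30 or 2.10, so it cannot show which case applies.

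**Conclusion.** The point holds in limited form. Up to about 80 of 390 Week 12 HAM-A scores may be missing, an unstated share for reasons tied to response, and the plan gives no means of observing them. If loss is both unequal between arms and related to response, the filled drug-placebo difference can be wrong in either direction: 1.3 points too low at 15%/30% loss, 1.3 too high at 25%/10%, against a planned difference of 4. Those sizes assume no change in withdrawn subjects and fall to about 0.4 points if they improve by 6. The loss splits are illustrations; the documents give none. With equal loss and equal change in withdrawn subjects there is no such bias, since filled and true differences are both 3.2.

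Changing the fill rule is necessary but not sufficient, because leaving the gaps empty does not supply the outcomes of those who left for lack of efficacy. This should be changed, mainly because the remedy is cheap.

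**What to change.** Leave every stopping criterion as it is. Add that meeting one ends study drug but not follow-up, unless consent is withdrawn. Then:

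- do HAM-A at withdrawal and at the remaining scheduled visits, at least Week 12;
- record any prohibited medicine started, with its date;
- use these values in the Full Analysis Set, and state that this analysis estimates the effect regardless of stopping drug;
- keep the Per Protocol analysis alongside;
- do not fill the remaining gaps with the pooled mean.

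Cost: a protocol amendment and one to three visits per subject, on dates already in the schedule, for at most about 80 subjects, with the same staff and scale. No increase in sample size is needed to collect these values. The drawback is that the estimate may be smaller, because off-drug values are included.
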